The EXAMINATION EXTEND study aims to examine patient and device-oriented endpoints after ten years of follow-up in STEMI patients randomly assigned to EES or BMS in the EXAMINATION trial focusing on the differences between 5 and 10 years of follow-up.

7. Methods

The EXAMINATION TRIAL is a multicentre, multinational, prospective, randomised, two-arm, single-blind, controlled trial performed in patients with STEMI (clinicaltrials.gov number: NCT00828087). It has randomized 1.498 patients to receive

either an EES (751 patients) or a BMS (747 patients). At 5 years, complete clinical follow-up was obtained in 97.3% in both arms.

A total of 12 centers in 3 countries were involved in the trial. All these centers have been contacted to prolong follow-up up to 10 years. Nine Institutions agreed to participate in this project for a total of 1.450 patients expected at 10-year follow-up.

An excel sheet was sent to all the centers to be fulfilled with 10-year follow-up of the patients included, collecting all-cause death, any myocardial infarction and any revascularization occurred between 5 and 10 years.

The primary endpoint of the study is the patient-oriented combined endpoint of all-cause death, any myocardial infarction or any revascularization at 10 year according to the Academic Research Consortium (ARC). ²⁴ The secondary endpoint of the study is the device-oriented combined endpoint of cardiac death, target vessel myocardial infarction or target lesion revascularization at 10-year. ²⁴ In addition, stent thrombosis (according to the ARC definitions²⁴) will be collected.

A clinical event committee, whose members are masked to the assigned stent, will independently adjudicate all deaths, potential myocardial infarctions, stent thrombosis, and revascularization procedures. We expect a 40% incidence of events for a total of 400 events to be adjudicated.

8. Inclusion and exclusion criteria

There are no relevant inclusion and exclusion criteria for the current extended study since this pertains to a follow-up of patients already enrolled in the main EXAMINATION trial.

9. Population

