The population was the patients enrolled in the EXAMINATION trial. The study had broad inclusion and few exclusion criteria. Any patient presenting with STEMI with the following electrocardiogram criteria: at least 1 mm in two or more standard leads or at least 2 mm in two or more contiguous precordial leads or left bundle-branch block that was not known to be old, within the first 48 h after the symptoms onset requiring emergent percutaneous coronary intervention with a vessel size ranging between 2·25 mm and 4·0 mm without other anatomical restrictions could be included. Exclusion criteria were age younger than 18 years, pregnancy, patients with known intolerance to aspirin, clopidogrel, heparin, stainless steel, everolimus or contrast material, and patients on chronic treatment anti-vitamin K agents, and STEMI secondary to stent thrombosis. The patients were enrolled at 11 sites in 3 countries.

10. Endpoints

The prespecified primary endpoint of the EXAMINATION EXTEND study are the patient-oriented combined endpoint of all-cause death, any myocardial infarction, or any revascularization at 10 year according to the Academic Research Consortium (ARC) definition.²⁴ Secondary endpoints included the device-oriented combined endpoint of cardiac death, target vessel myocardial infarction (MI), or target lesion revascularization (TLR)²⁴; all-cause and cardiac death; target vessel revascularization (TVR); and, stent thrombosis (according to ARC definitions).²⁴ Detailed descriptions of the study endpoints and definitions have been reported previously.²⁵ Vital status will be verified in all patients. Independent study monitors (ADKNOMA, Barcelona, Spain) will verify the adequacy of the extended follow-up in 50% of all the patients included, together with all the reported events on-site. All events will be

adjudicated and classified by an independent event adjudication committee blinded to the treatment groups (Barcicore Lab, Barcelona, Spain).

11. Data collection

The EXAMINATION trial protocol was approved by the institutional review board of all 85 sites and is consistent with the International Conference on Harmonisation Guidance of Industry E6 Good Clinical Practice, the Declaration of Helsinki local regulations. Written consent was obtained from all participating patients when enrolled at baseline, for the duration of 5-years of follow-up.

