Data collection for the entire cohort of patients will be performed via principal investigators at participating centers. Each center will be contacted by email to gather long-term results for the patients at that particular center. Teleconference calls will be performed for the site training and clarify issues.

The ethical committee will approve the protocol of the coordinating center (Ethics Committee for Drug Research, Hospital Clínic of Barcelona, Spain). After that, the study protocol approval by each site medical ethics committee approval will be requested. Once obtained, survival status and clinical outcomes will be retrospectively collected. Patient records at hospitals will be checked to assess survival status. If survival is unclear from the patient record, national death registries will be consulted to complete information on death and the specific date. In case a patient has died, the cause of death will be determined from medical records.

12. Data base information

An anonymous database of patients enrolled in the EXAMINATION trial is already available with baseline characteristics, procedural characteristics, and outcome data. All patients included in the database have been assigned a unique study number. Patient information of the patient assigned this study number is only available at individual sites. Local principal investigators will send anonymous data identifiable per unique study number to the study coordinator and principal investigator (dr. [name]). A central database will be stored at the Institut d'Investigacions Biomèdiques August Pi i Sunyer (IDIBAPS). In comparison to the already existing database, this database will be edited only by changing the duration of follow-up, date of death if this occurred, and the cause of death.

[figure not shown]
13. Statistics

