A specific statistical plan analysis document will be provided. All analyses will be performed according to the intention-to-treat principle. Patients with missing follow-up data will be included in the analysis and censored at the time they are lost to follow-up or at 5-year if their recruiting hospital did not participate in the 10-year follow-up. We will analyze the primary endpoint of 10-year patient-oriented composite endpoint using Kaplan-Meier curves, with a log-rank p-value to test between-groups differences. We will use Cox proportional hazards models to estimate hazard ratios (HRs) with 95% confidence intervals (CI) comparing EES with BMS. We will do landmark analyses in the overall population, setting the landmark points at 1 and 5 years to distinguish the EXAMINATION trial results from the extended follow-up of the EXAMINATION EXTEND study. The same will be done for the device-oriented composite endpoint and the other secondary endpoints. Subgroup analyses will include the following specified

variables: gender, age >75 , presence of diabetes, post-PCI TIMI <3 , multivessel disease, ejection fraction $<30\%$, Killip class $>I$, ST-segment resolution $>70\%$, use of aspiration thrombectomy catheters, primary PCI (STEMI $<12h$), and left anterior descending as the infarct-related artery.

14. Time Schedule

EXAMINATION EXTEND Timeline

15. Administrative aspects and publication

Confidentiality and handling and storage of data and documents

Data will be stored on the Hospital Clínic local network drive with automatic overnight back-up. Stored data regarding patients and personnel included in this study can only be accessed by the investigators and the Ethics Committee for Drug Research of the Hospital Clínic (including Hospital Clínic auditors and monitors, if necessary). The processing, communication, and transfer of personal data of all participants will comply with EU Regulation 2016/679 of the European Parliament and of the Council of 27

April 2016 on the protection of individuals concerning the processing of personal data and the free movement of data, which must be complied with from 25 May 2018. If published in scientific journals or presented at scientific meetings, any information from this study will not reveal patient identity. Data will be stored for a maximum of 25 years after ending the study. Collected data will be secured against unauthorized access and stored and secured by the Hospital Clínic of Barcelona.

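### One censoring rule for all endpoints, combined with registry-found deaths, permits outcome-dependent follow-up; the protocol should fix separate vital-status and clinical follow-up dates

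*Protocol*

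**What the plan says.** All references are to the protocol; the statistical analysis plan was not available.

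- **Section 13 (Statistics)** gives one rule: "Patients with missing follow-up data will be included in the analysis and censored at the time they are lost to follow-up". Its only exception is for hospitals that stayed out of the extension, whose patients are censored at 5 years. It describes Kaplan-Meier, log-rank, Cox and landmark analyses (1 and 5 years) for the primary endpoint and extends them to the device-oriented composite and the other secondary endpoints. It gives no separate censoring date for death.
- **Section 11 (Data collection)** adds a second source: "If survival is unclear from the patient record, national death registries will be consulted to complete information on death and the specific date".
- **Section 12 (Data base information)** says of the central database that "this database will be edited only by changing the duration of follow-up, date of death if this occurred, and the cause of death". Only one follow-up duration is named.
- **Section 10 (Endpoints)** defines the primary endpoint as "the patient-oriented combined endpoint of all-cause death, any myocardial infarction, or any revascularization at 10 year", lists all-cause and cardiac death among the secondary endpoints, and promises: "Vital status will be verified in all patients".

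No section gives the censoring date for a patient lost to clinical contact whom the registry does not show as dead. None says whether a registry death after clinical loss counts in the composites.

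**The concern.** Kaplan-Meier and Cox analyses need censoring that does not depend on the outcome. The most direct implementation of Sections 11 to 13 breaks this. Take two patients who both leave clinical contact at year 6. One dies at year 9 and is found in the registry: the death is entered at year 9, and the patient is at risk for nine years. The other is alive at year 10: under the Section 13 rule the patient is censored at year 6. Lost patients who die keep their person-time and their event, while lost survivors give up their person-time. The risk set is too small and the event rate too high.

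At stake are the absolute 10-year rates and the rates after the 5-year landmark, the period that Sections 5 and 6 single out. There is also a choice left open until the data are seen: whether registry-only deaths enter the primary endpoint.

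**Working it through.** **Plan figures.** The protocol states no late-loss rate and no expected mortality, so there is no figure on this point to reproduce. Its one event forecast (40% incidence, 400 events) does not fit its own denominator (0.40 × 1,450 = 580). That is a separate matter; only the 40% is used here.

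**Inputs from the protocol (Section 7).** 1,498 randomised (751 and 747); 97.3% complete follow-up at 5 years in both arms, so 2.7% lost in each; composite incidence 40%.

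**Assumptions.** 10-year mortality D of 20% (range 15-25%); constant hazards; the registry finds every death; early loss uniform over years 0-5; late loss of 0 to 20%.

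**Step 1: formula for death.** Let S(t) be true survival, λ = −ln(1 − D)/10, and F(t) the proportion whose clinical contact would end by t. Only lost patients who survive to year 10 are removed from the risk set, so the apparent hazard is

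h(t) = λS(t) / [S(t) − F(t)S(10)].

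**Step 2: documented loss only.** With D = 20%, λ = 0.02231. With F rising to 0.027 at year 5 and flat after that, the excess cumulative hazard is 0.0013 in years 0-5 and 0.0029 in years 5-10, total 0.0042. Apparent mortality is 1 − 0.80 × e^(−0.0042) = 20.3%. At D = 15% and 25% it is 15.3% and 25.4%. The overstatement is therefore 0.3 to 0.4 points, and about 31% of it (0.0013/0.0042) arises before year 5.

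**Step 3: adding late loss, uniform over years 5-10.** Simulation with 1,000,000 patients per scenario, true death 20%:

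| Late loss (assumed) | Apparent 10-year death |
|---|---|
| 0% | 20.3% |
| 2.7% | 20.4% |
| 5% | 20.6% |
| 10% | 20.8% |
| 20% | 21.3% |

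At 20% late loss the overstatement is 1.1 to 1.7 points over D = 15-25%; the formula gives 16.1%, 21.3% and 26.6%. Censoring every lost patient at loss, or carrying verified survivors to year 10 for death, returns the true value.

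**Step 4: all late loss at year 5 (less favourable).** Here S(5) = 0.8944. Mean person-time over years 5-10, per patient alive at year 5, is 0.1056/0.02231 = 4.731 years. A lost fraction p removes p × 5 × 0.8944 = 4.472p years from it and no deaths. The late rate is inflated by 4.731/(4.731 − 4.472p), and apparent 10-year death is 1 − 0.8944² × (1 − p)/(1 − 0.8944p):

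| p | Late death rate | 10-year death |
|---|---|---|
| 5% | +5% | 20.4% |
| 10% | +10% | 20.9% |
| 20% | +23% | 22.1% |

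**Step 5: primary composite, true 40% (simulated).** Counting registry deaths and censoring lost survivors at loss gives 40.2-40.4% at the documented loss and 40.8-41.4% with 20% late loss. Carrying registry-alive patients to year 10 errs the other way, because their MI and revascularization are unobserved: 39.5-39.8% and 38.6-39.1%. Censoring all lost patients at loss returns 40%.

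**Step 6: treatment comparison.** With equal loss and a true ratio near 0.80, the rate ratio moves by at most 0.002. With late loss of 10% v 5%, or 20% v 10%, the death ratio moves by about 0.01 to 0.02. An extreme case, 15% v 5% all lost at year 5 with no true effect, gives a late death ratio of 1.165/1.050 = 1.11.

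**The case against.** The strongest reply is Section 10. If vital status really is verified in all patients, a lost survivor is known to be alive, is not missing for death, and can have follow-up extended under Section 12. On that reading there is no mortality bias. This stands as a possible reading, so a reader who infers that late mortality will be overstated goes further than the documents allow: no section says that a patient verified alive is censored back at last contact. But Section 13 does not take up the verified status either. It names no verification date and applies one rule to death and non-fatal endpoints alike. Verified vital status also leaves the composites open, because a death registry supplies no MI or revascularization.

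The second reply is that censoring detail belongs in the analysis plan. That would answer a mere silence. Here the protocol does state a rule, and it fits poorly with the registry stream.

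The third concerns size. The sampling standard error of a 20% risk with 750 patients is √(0.2 × 0.8/750) = 1.5 points, well above 0.3 to 0.4, and losses of 10-20% are not documented. This stands, and keeps the point modest. Two further inferences also fail. The bias is not confined to years 5-10, since the documented loss came before year 5. A biased hazard ratio needs unequal loss, while 5-year completeness was the same in both arms. Nor does the 5-year cut at non-participating hospitals cause the problem: it is set by hospital, not by outcome, provided no later registry deaths from those hospitals are counted.

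For the device-oriented composite, a registry-only death may lack a cause, since Section 11 takes cause of death from medical records. No size was computed for it.

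**Conclusion.** The point holds as a defect in the wording of the rules, with a small documented effect. Sections 11 to 13 together permit follow-up that depends on outcome. If implemented that way, absolute death rates are overstated by about 0.3 to 0.4 points and the primary composite by 0.2 to 0.4 points at the documented 2.7% loss. At an assumed 20% late loss the overstatement of death is about 1 to 2 points (1.1 to 1.7 if late loss is spread over years 5-10, 2.1 if all at year 5 with 20% true mortality). The between-arm ratio is almost unaffected unless loss differs by arm. These figures rest on constant hazards, complete registry capture of deaths, and true mortality of 15-25%. The documents do not show that the bias will occur, or that the treatment effect is biased.

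**What to change.** Record two dates per patient on the site sheet: the date on which vital status was verified (record or registry search) and the date of the last clinical record. Then replace the single rule in Section 13, or state in the analysis plan:

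1. **All-cause death:** everyone not found dead is censored at the verification date, at most 10 years. At non-participating hospitals follow-up stops at 5 years and no later registry death is counted.
2. **Composites:** one stated rule for deaths after the last clinical-record date, applying the same follow-up window to patients found dead and patients found alive.
3. **Sensitivity analysis:** the alternative handling, with those deaths counted if the main analysis leaves them out, or left out if it counts them.

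Which handling is primary for the composites is a trade-off. Leaving out known deaths sits awkwardly with an endpoint that includes all-cause death; counting them means follow-up without MI and revascularization data. The choice matters less than making it before the late outcomes are seen. The cost is two date columns, one paragraph and one extra analysis.

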Percutaneous coronary intervention (PCI) is the standard of treatment in ST-elevation myocardial infarction (STEMI) when performed in experienced Institutions within adequate time delay after the symptoms onset.¹ ST-segment elevation myocardial infarction (STEMI) represents the paradigm of a thrombotic milieu and a challenging clinical scenario to test new intracoronary devices.² In this clinical setting, first generation drug-eluting stents (DES) have demonstrated to reduce clinical and angiographic restenosis compared to BMS.³⁻⁹ Conversely, these benefits were counterbalanced by an increased risk of very late stent thrombosis.¹⁰⁻¹³ These safety concerns were confirmed by autopsy and intravascular imaging studies, showing evidence of incomplete endothelialization, delayed arterial healing, and vessel remodeling due to chronic inflammation in patients with very late stent thrombosis.¹⁴⁻¹⁹ Development of neatherosclerosis has been identified as an important player in the pathophysiology of the occurrence of very late events.

Second generation everolimus-eluting stent (EES; XienceTM V; Abbott Vascular, Santa Clara, CA) has been designed with a thin (7.8 μ m) non-adhesive, durable, biocompatible acrylic polymers and fluorinated copolymer.²⁰ As compared with first generation DES, the XienceTM V stent was able to reduce both the restenosis and the

thrombosis rates in randomised controlled trials and meta-analyses.^{21,22} The EXAMINATION (clinical Evaluation of the Xience-V stent in Acute Myocardial INfArcTION) all-comers trial was designed to compare clinical outcomes between EES and BMS in STEMI patients. At 5-year follow-up it demonstrated clinical superiority of EES over a BMS in patients with STEMI requiring primary percutaneous coronary intervention.²³

Currently available data on clinical outcome beyond 5 years are scant, especially in an important clinical scenario such as STEMI. It is therefore unknown if advantages of second-generation DES are maintained at very long-term follow-up, when incidence of neotherosclerosis is high and it may play an important role in the pathophysiology of the occurrence of very late events.

We herein sought to compare 10-year clinical outcomes of EES vs. BMS in the EXAMINATION trial, focusing on differential effects between the first 5 years and subsequent years.

6. Objectives

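### The 5-year landmark, the only analysis that isolates the study's focus period, compares groups selected by an outcome the stent had already changed, so its hazard ratio should be labelled descriptive and not carry the late-benefit conclusion alone.

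*Protocol*

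**What the plan says.** Two sections of the protocol make the late period the point of the study. Section 5 (Background) closes with the aim of comparing 10-year outcomes, "focusing on differential effects between the first 5 years and subsequent years". Section 6 (Objectives) repeats it: "focusing on the differences between 5 and 10 years of follow-up". Section 5 also reports the earlier result: "At 5-year follow-up it demonstrated clinical superiority of EES over a BMS".

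Section 13 (Statistics) opens with the rule "All analyses will be performed according to the intention-to-treat principle". It then says "We will analyze the primary endpoint of 10-year patient-oriented composite endpoint using Kaplan-Meier curves", with a log-rank test and Cox HRs. These run over the whole 10 years. The one analysis that splits the follow-up is the landmark, "setting the landmark points at 1 and 5 years to distinguish the EXAMINATION trial results from the extended follow-up", to be repeated for the device-oriented composite and the other secondary endpoints. Section 13 does not say who enters the 5-year landmark set and gives no caveat on reading its HR. It refers to a separate statistical plan, which is not at hand.

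**The concern.** A landmark analysis of a first-event endpoint usually keeps only patients who are event-free at the landmark. If EES prevented events in years 0 to 5, some high-risk patients who would have left the risk set on BMS are still in it on EES. The two groups that start year 5 are then no longer the randomised groups, and the EES group carries more residual risk. A 5-10-year HR nearer 1 could be read as fading benefit, and one above 1 as late catch-up, although nothing had changed for any individual patient. A treatment-by-period term in a Cox model uses the same late risk sets, so it would not remove the problem. The 0-10-year HR averages over the change of interest.

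This is more than a detail left to the statistical plan, because the protocol itself fixes both the landmark and its purpose.

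**Working it through.** **Figures in the protocol.** There are 751 EES and 747 BMS patients, with 1450 expected at 10 years (section 7). It gives no 5-year rates, no 5-year HR and no measure of heterogeneity, so there is no planned landmark figure to reproduce. Section 7 mentions a 40% incidence and 400 events, but 0.40 × 1450 = 580, and 400/0.40 = 1000. The 40% is not defined as a pooled first-event risk. It is used below as an assumption only.

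**Model (assumed).** Individual risk varies with gamma frailty of variance θ, and the individual HR r is constant. Then S_BMS(t) = (1 + θλt)^(−1/θ) and S_EES(t) = (1 + θrλt)^(−1/θ). The baseline hazard λ is solved so that the mean of the two 10-year risks is 40%.

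**Worked case, r = 0.80, θ = 1 (λ = 0.0744).**
- Event-free at 5 years: BMS 1/1.372 = 0.729, EES 1/1.298 = 0.771.
- Event-free at 10 years: BMS 1/1.744 = 0.573, EES 1/1.596 = 0.627.
- 0-5-year HR: ln 0.771 / ln 0.729 = 0.82.
- 5-10-year landmark HR: ln(0.627/0.771) / ln(0.573/0.729) = 0.86.
- Mean residual frailty at 5 years equals 0.729 in BMS and 0.771 in EES when θ = 1, so it is 6% higher in EES. The HR at the moment of the landmark is therefore 0.80 × 1.057 = 0.85. The remaining move to 0.86 is depletion that continues after year 5.

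**Landmark HR across θ**

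| True constant HR | θ = 0 | θ = 0.5 | θ = 1 | θ = 2 |
|---|---|---|---|---|
| 0.80 | 0.80 | 0.83 | 0.86 | 0.91 |
| 0.60 | 0.60 | 0.66 | 0.71 | 0.80 |

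**Against sampling error.** If 25% have an event by year 5 (assumed) and 40% by year 10, late events are 0.15 × 1450 ≈ 218, and SE(log HR) ≈ 2/√218 ≈ 0.14. For r = 0.80 the shift is ln(0.861/0.80) = 0.073 at θ = 1, about 0.5 SE, and ln(0.907/0.80) = 0.125 at θ = 2, about 0.9 SE.

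**Wider assumptions.** Let the BMS risk be 20-30% at 5 years and 30-43% at 10 years, the observed early HR 0.7-0.9, and θ 0-2. With no true late effect the landmark HR is 1.00 to 1.19, and 1.02 to 1.07 in the middle cases (early HR 0.8, θ 0.5-1). With a true late HR of 0.80 it is 0.80 to 0.99, and 0.82 to 0.87 in the middle cases. A simulation with one million patients per arm (θ = 1, early individual HR 0.8) gave 1.05 and 0.86 for true late HRs of 1.00 and 0.80.

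**Risk differences in all randomised patients (r = 0.80, θ = 1).** The benefit is 77.1 − 72.9 = 4.2 points at 5 years and 62.68 − 57.33 = 5.35 points at 10 years. It still widens while the HR appears to weaken from 0.82 to 0.86.

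**Can the change in risk difference replace the landmark HR?** The change is about 1.17 points. Late risks are 0.155 (BMS) and 0.144 (EES), so with full follow-up of 1498 patients its SE is √(0.155×0.845/747 + 0.144×0.856/751) = 1.84 points, and z = 1.17/1.84 ≈ 0.6. For the landmark, z = −ln 0.861/0.135 ≈ 1.1. The change also misleads in its own way. With θ = 0, an early HR of 0.80 and a late HR of exactly 1 (BMS event-free 0.752 at 5 years and EES 0.796), the difference is 4.4 points at 5 years. Both arms then shrink by the same factor, so it falls to 4.4 × 0.752 = 3.3 points at 10 years, while the landmark HR is 1.00.

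**The case against.** The strongest reply has four parts.

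- **The statistical plan may handle it.** The landmark set and caveats may be defined there, and the protocol's stated purpose is only to separate two periods. Nowhere does it call the late HR causal. This stands as a limit on the charge: the protocol makes no false claim. It does, however, assign its focus question to this one analysis.
- **The bias is conditional.** It is exactly zero without unmeasured heterogeneity, and below one SE in the middle cases. Part of the shift is attenuation already present in years 0-5 (0.82, not 0.80), and part is depletion after year 5. This stands. Still, some variation in risk is hard to doubt in a broadly enrolled STEMI population, the expected direction is against EES, and the confidence interval does not cover it.
- **The all-randomised curves are already planned.** Cumulative risks at 5 and 10 years can be read from them. True, but no risk difference or interval is specified, and nothing ties the late-benefit conclusion to them.
- **The change in risk difference is a poor main estimate of late effect.** The check above confirms this, so it should be supportive only.

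A reader might infer that the late HR is known to be biased, or that the 10-year result is compromised. The documents support neither: they give nothing from which a bias can be established, and the primary comparison does not condition on status at 5 years.

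**Conclusion.** The point holds as an improvement to a fixed analysis choice. It is not a demonstrated error in the result. In its usual event-free form, the 5-year landmark conditions on a post-randomisation outcome that the protocol itself says EES had changed. If patients differ in unmeasured risk, the late HR is expected to move towards or above 1. With a constant HR of 0.80 and a 40% pooled 10-year risk, the move is to 0.83-0.86 for frailty variance 0.5-1 and to 0.91 for variance 2, against an SE of about 0.14. Heterogeneity, event rates and the event-free risk set are all assumptions.

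The landmark HR remains a valid description of patients still at risk. What it cannot do alone is show that benefit was lost or maintained. Whether the advantage is still present at 10 years can be answered by a randomised contrast.

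**What to change.** - Keep the landmark HRs, and label them as descriptive of patients still at risk at the landmark.
- Beside them, report Kaplan-Meier risk differences (EES minus BMS) with 95% CIs at 5 and at 10 years in all randomised patients, for the patient-oriented and device-oriented endpoints.
- State that loss or persistence of benefit will not be concluded from the landmark HR alone.
- The 5-to-10-year change in risk difference may be added as supportive. It should not be the main estimate of late device effect.

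The cost is a few lines of text and code, with no new data. The downside is a few more estimates to report, with wide intervals.

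### Section 13 appears to carry Kaplan-Meier over to four secondary endpoints with competing deaths, where 1-KM would modestly overstate 10-year risk

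*Protocol*

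**What the plan says.** Protocol section 13 (Statistics) starts with the primary endpoint: "We will analyze the primary endpoint of 10-year patient-oriented composite endpoint using Kaplan-Meier curves, with a log-rank p-value to test between-groups differences". It then names Cox models for the hazard ratio of EES against BMS, and continues: "We will do landmark analyses in the overall population, setting the landmark points at 1 and 5 years". The secondary endpoints get one sentence: "The same will be done for the device-oriented composite endpoint and the other secondary endpoints". No other sentence in the protocol gives them a method.

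Section 10 (Endpoints) defines the device-oriented composite with cardiac death only, alongside target vessel infarction and target lesion revascularization. The other secondary endpoints are "all-cause and cardiac death; target vessel revascularization (TVR); and, stent thrombosis (according to ARC definitions").

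On censoring, section 13 says: "Patients with missing follow-up data will be included in the analysis and censored at the time they are lost to follow-up", or at 5 years where the recruiting hospital did not join the extension. It has no rule for a death that is not part of the endpoint. Competing risks and cumulative incidence are not mentioned anywhere. A separate statistical analysis plan is announced; it was not available for this review.

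**The concern.** Kaplan-Meier suits the primary composite because every death counts as an event. Four of the secondary endpoints differ:

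| Endpoint | Competing event |
|---|---|
| Device-oriented composite | Non-cardiac death |
| Cardiac death | Non-cardiac death |
| TVR | Any death |
| Stent thrombosis | Any death |

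All-cause death, also a secondary endpoint, has no competing event.

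A Kaplan-Meier curve for these four normally censors the competing deaths, that is, it treats patients who have died as if they could still have the event. The protocol does not state this censoring; it follows from the method. The curve then estimates risk in a hypothetical setting without competing death, not the proportion of patients who actually have the event by 10 years.

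What is at stake is the absolute-risk display: the four curves, and any incidence or risk difference read from them. The gap widens as deaths accumulate, so it matters more at 10 years than it did at 5.

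**Working it through.** **Direction.** Let H1(t) be the cumulative cause-specific hazard of the endpoint and S(t) the probability of being free of both the endpoint and the competing death. With competing deaths censored, 1-KM = 1 − exp(−H1). The actual risk is the integral of S(t) dH1(t). Since S(t) ≤ exp(−H1(t)), 1-KM is never below the actual risk, and is strictly above it once endpoint events follow competing deaths. This needs no assumed rate.

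**Inputs for size.** From section 7, the arms are "either an EES (751 patients) or a BMS (747 patients"). The protocol gives no rate for any of the four endpoints, nor for cardiac or non-cardiac death, so every rate below is an assumption and there is no protocol figure to reproduce.

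**Formula, constant hazards.** With K the 10-year 1-KM value and C the 10-year competing mortality (on the same 1 − exp(−H) scale), H1 = −ln(1 − K), H2 = −ln(1 − C), and

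actual risk = H1/(H1 + H2) × [1 − (1 − K)(1 − C)].

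Example, device-oriented composite, K = 20%, C = 16%: H1 = 0.2231, H2 = 0.1744; 0.2231/0.3975 × (1 − 0.80 × 0.84) = 0.561 × 0.328 = 18.41%. The excess is 20.00 − 18.41 = 1.59 points.

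The last column is a front-loaded case: 50% of the endpoint hazard and 10% of the competing hazard in year 1, piecewise constant.

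| Endpoint | Assumed K | Assumed C | Actual risk | Excess, constant (points) | Excess, front-loaded (points) |
|---|---|---|---|---|---|
| Device composite | 15% | 5% | 14.63% | 0.37 | 0.22 |
| Device composite | 20% | 16% | 18.41% | 1.59 | 0.93 |
| Cardiac death | 8% | 5% | 7.80% | 0.20 | 0.12 |
| Cardiac death | 12% | 16% | 11.03% | 0.97 | 0.57 |
| TVR | 10% | 15% | 9.24% | 0.76 | 0.45 |
| TVR | 16% | 25% | 13.96% | 2.04 | 1.21 |
| Stent thrombosis | 2% | 15% | 1.85% | 0.15 | 0.09 |
| Stent thrombosis | 4% | 25% | 3.48% | 0.52 | 0.31 |

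(The actual-risk column is for constant hazards.) A second grid, which fixes the actual risks instead of 1-KM and allows wider values, gives at most 2.6 points: TVR 16% with 25% dying first.

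**Landmark window, 5 to 10 years, constant hazards.** K = 3%, C = 8% gives 2.88% (0.12 points). K = 8%, C = 15% gives 7.39% (0.61 points).

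**Arm difference, TVR.** Assume K = 12% (EES) and 16% (BMS), a Kaplan-Meier difference of 4.0 points.

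| Mortality EES / BMS | Actual difference, constant (points) | Front-loaded (points) |
|---|---|---|
| 15% / 15% | 3.71 | 3.83 |
| 20% / 20% | 3.61 | 3.77 |
| 25% / 25% | 3.50 | 3.71 |
| 15% / 20% | 3.29 | 3.58 |
| 20% / 25% | 3.18 | 3.52 |
| 20% / 15% | 4.02 | 4.02 |
| 25% / 20% | 3.93 | 3.96 |

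The difference need not shrink; it depends on which arm has more deaths. The largest shift is 4.00 − 3.18 = 0.82 points. The standard error of the difference, ignoring censoring, is √(0.12 × 0.88/751 + 0.16 × 0.84/747) = 1.79 points, so that shift is 0.82/1.79 = 0.46 standard errors.

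**The case against.** The strongest reply is that the curve estimator for secondary endpoints belongs in the statistical analysis plan, which is promised and may already specify cumulative incidence. That cannot be excluded. But the protocol is not silent here: it chooses a method and extends it to endpoints of a different structure. If the analysis plan already handles this, the action shrinks to aligning one sentence of the protocol.

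Second, the carry-over sentence follows directly on the landmark sentence and could mean only the landmark analyses. This stands as a real ambiguity. On that reading, though, the secondary endpoints would have no stated curve, test or effect measure over the whole follow-up, so the wider reading is the more natural one. On the narrow reading the point applies only where the landmark results are shown as Kaplan-Meier curves.

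Third, the stated inferential measures are a log-rank p-value and hazard ratios, both unharmed, and the protocol does not say that absolute risks will be read from the secondary curves. That is correct and keeps the point minor. Readers of a 10-year outcome study will nonetheless take incidences from its curves. For a rare endpoint the relative error is not trivial: 4% shown against 3.48% actual stent thrombosis is an overstatement of 0.52/3.48, about 15%.

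Fourth, the size rests wholly on assumed rates and one chosen front-loading pattern. That also stands. Only the direction is certain.

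**Conclusion.** The point holds as a minor one. If the carry-over includes Kaplan-Meier and competing deaths are censored, 1-KM lies above the actual 10-year risk for all four endpoints. On the main assumed ranges the excess is about 0.2 to 2.0 points under constant hazards, and 0.1 to 1.2 when half the endpoint hazard falls in year 1. The effect on the assumed TVR arm difference stays under half a standard error, so no reversal of a conclusion is expected. The primary composite and all-cause death are untouched, and the log-rank tests and Cox hazard ratios remain valid as comparisons of cause-specific hazards. Confidence is moderate, because the reading of one sentence is open and the analysis plan was not seen.

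**What to change.** In section 13:

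- State whether the carry-over to secondary endpoints covers the curves, log-rank and Cox, or only the landmark analyses.
- For the device-oriented composite, cardiac death, TVR and stent thrombosis, replace 1-KM with Aalen-Johansen cumulative incidence curves, overall and in any landmark curves. Name the competing event: non-cardiac death for the first two, any death for the last two.
- Keep log-rank and Cox for these endpoints, and label the hazard ratio cause-specific.
- Leave the primary composite and all-cause death on Kaplan-Meier.

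The cost is one or two sentences and a standard software routine. Section 11 already plans to obtain the date of death, and on cause it says: "In case a patient has died, the cause of death will be determined from medical records". No further data are needed. The drawback is that the new incidences will be slightly lower than earlier Kaplan-Meier figures from this trial and not directly comparable with them, so both should be tabulated.
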